## **I. RATIONALE AND PURPOSE OF STUDY**

### **a. Background:**

Mental disorders among children and adolescents have been on the rise, and have reached a prevalence rate of 16.5% in the U.S. (Twenge, Cooper, Joiner, Duffy, & Binau, 2019; Whitney & Peterson, 2019). Preventative approaches are effective in reducing the adolescent mental health burden, particularly when they target specific risk and protective factors for mental health (Kieling et al., 2011). One specific risk factor for future mental health problems in adolescence is elevated, chronic stress (Anderson et al., 2014), which has rarely been evaluated as an outcome variable in interventions (Feiss et al., 2019) with the exception of school-based stress management interventions. Stress is a growing concern for teens in the U.S., as adolescents have reported higher levels of stress than they perceive to be healthy, levels that are often higher than those reported by adults, and many reported increasing levels of stress (Anderson et al., 2014). What stress-focused interventions exist tend to rely on simple stress reduction techniques (Carter & Garber, 2011; Dozois, Seeds, & Collins, 2009) and these have had limited efficacy. However, adolescent stress may stem from negative cognitions, thus general mental health interventions that incorporate therapeutic approaches to improving negative cognitions may more effectively reduce adolescents' perceived stress levels. Rumination is a transdiagnostic, cognitive process strongly associated with stress, which also exacerbates the negative effects of stress among adolescents (Topper, Emmelkamp, Watkins, Ehring, 2017). There is evidence that both rumination and perceived stress can be reduced with interventions based on Cognitive-Behavioral Therapy (CBT) and mindfulness, suggesting an approach drawing on several therapeutic traditions that target specific positive and negative factors may be the most beneficial (Mazzer & Linton, 2019; Bessette et al., 2020). Unfortunately, little research on adolescent interventions assesses both stress and rumination; therefore, testing an intervention aiming to reduce stress and rumination is warranted.

**b. Rationale:** Because of the dearth of interventions aiming to reduce stress and rumination in adolescence, particularly ones that are scalable and low-cost, further exploration and dissemination of mental health interventions is warranted.

Happify for Teens, a digital product that aims to improve well-being, may be particularly useful for adolescents in reducing perceived stress and rumination due to its holistic approach. Although previous studies have shown that Happify can improve resilience, subjective well-being, anxiety, and depression in adults (Parks et al., 2018; Parks et al., 2020), it has never been tested in a younger age group (ages 13-17). The proposed study will build on previous research by examining

the efficacy of Happify in a new population, and will potentially offer a valuable and accessible mental health resource to teens.

**c. Purpose:** The purpose of this study is to examine whether a digital product, called “Happify for Teens”, can successfully reduce perceived stress and rumination, and improve other outcomes including: sleep disturbance, loneliness, and optimism, for teenagers ages 13-17, when compared to a waitlist control condition. Happify is delivered online and rooted in various therapeutic traditions, including CBT, positive psychology, and mindfulness-based stress reduction. It provides users with tracks and activities that teach skills involving savoring (e.g., mindfulness-based activities), thanking (e.g., gratitude-based activities), aspiring (e.g., optimism and goal-setting activities), giving (e.g., kindness and forgiveness activities), empathizing (e.g., self-compassion and perspective-taking activities), and reviving (e.g., physical activities), which aim to improve mental health. If found to be effective, Happify for Teens will be an accessible and cost-effective resource for teen stress reduction and general mental health.

**d. Nature of Study:** The nature of this study is confirmatory and exploratory. We will be testing the hypothesis that using the Happify platform will result in greater decreases in perceived stress and rumination over an 8-week period compared to a waitlist control, with users who complete more activities experiencing more improvement. We also aim to explore the effects of Happify on several factors, including: sleep disturbance, loneliness, and optimism. To do this, we will employ a longitudinal randomized design. Participants will be randomly assigned to either the Happify experimental condition or the waitlist control condition after meeting inclusion criteria and taking a baseline assessment. Those in both conditions will be asked to complete assessments at 4 weeks (mid-point), after the 8-week intervention period (immediate post-test), and 1-month post intervention. Participants will be adolescents aged 13-17 with elevated levels of rumination and stress who are recruited online.

## **II. PROCEDURES INVOLVED**

### **a. Study Design:**

- i. This study will build on Happify’s existing recruitment strategies and will advertise to parents on social media and existing Happify users who indicate they have adolescents. Parents who take interest in having their child(ren) participate in this study will be directed to an online prescreen questionnaire via Qualtrics that will assess their child(ren)’s eligibility for the study by asking how many kids they have aged 13-17, their child(ren)’s age(s), country of residence, and previous Happify use. They will also be provided with a description of the study and what their child(ren) will be expected to do. If they are still interested and their

child(ren) meets these preliminary inclusion criteria, they will be asked to read and sign the consent form and check a box for each child that they want to participate. They will type their name and email, and child(ren)'s name and email so the child can complete their initial prescreener (in the event that a child does not have their own personal email address, parents will be instructed that they can provide a parent's email address and share the email with their child). After the prescreen, parents will be sent a Thank You email with a link to share the study with other parents who may be interested.

- ii. The Qualtrics prescreener link will then be sent to the child. It includes verifying their country of residence, age, and previous Happify use. They will also complete the Perceived Stress Scale (PSS) and Ruminative Responses Scale (RRS) to ensure their scores are above thresholds (PSS  $\geq$  10; RRS  $\geq$  14). Finally, the participant must agree to study duties, including: completing the baseline assessment, completing activities via Happify through a computer or smartphone, and being contacted throughout the 12 week period by Happify research staff. Participants are told that they may be assigned to a waitlist control and will not have access to the Happify platform until the end of the study but will still have to complete assessments. They are asked to check a box if they would be willing to continue with the study and not download Happify if assigned to the waitlist. We will ask participants to agree to not discuss the study with friends or family also participating in the study. If the child meets the inclusion criteria, they will be instructed that they'll receive an email inviting them to complete the first assessment (baseline assessment) on the following Monday or Thursday (whichever comes first). They must complete this assessment in order to qualify for the study, and must continue to meet thresholds for perceived stress and rumination, and pass at least one of 7 attention checks during the baseline assessment. This email will have instructions to set up a unique study ID that will be used throughout the study to link participant data across assessments and other data collections.
- iii. In this email, participants will be provided an assent form (through Qualtrics) which is shown at the beginning of the baseline assessment. If participants choose to, they will read and agree to a statement that they will provide honest and thoughtful responses throughout the study, and a separate statement agreeing not to discuss the study with any family or friends who may also be participating in the study. Participants must complete the baseline to be randomized to condition. Participants are

required to pass at least one of the attention checks in the baseline assessment. These attention checks require people to select a specific response option (e.g., for the PSS, an attention check item could instruct the participant to select “Never”, and this would vary across all assessments). Participants who complete and pass the baseline assessment on Qualtrics will be randomly assigned, via a Qualtrics randomization tool, to either the experimental or waitlist control group, and will receive an email or text (through Simple Text) with information detailing their condition on their corresponding start date. If they are in the experimental condition, they will also receive a link to download Happify. Both groups will complete assessments at 4 (mid-point), 8 (immediate post-intervention), and 12 weeks (one month post-intervention) via their preferred method of contact which was obtained in the baseline (e.g. email or text). All participants will be prompted to provide their user ID and complete the PSS, RRS - Brooding Subscale, LOT-R, PROMIS Pediatric Sleep Disturbance scale, and the RULS-8 via Qualtrics at each assessment point. Participants will also be asked at each assessment point if they have sought out help from other online platforms and what their current schooling situation is (fully remote, hybrid model, fully in person, home-schooled, or not in school). All of the assessments will have one attention check per questionnaire, which will instruct participants to select a specific response option to ensure they are reading questionnaire items and instructions carefully. The SLSS and PANAS-C-S will be administered only during baseline for scale validation purposes, and the experimental group will receive the Happify scale as part of the app experience every 2 weeks. In both cases, participants who do not qualify for the study will be thanked and alerted through Qualtrics that they do not qualify, and all their survey information will be deleted to protect their confidentiality. Participants who do not complete the baseline assessment will not go onto the study and will also have all of their information deleted.

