### III. RECRUITMENT

a. **Study Population:** This study will recruit adolescents aged 13-17 (Target  $N=800$ ) by advertising to parents on social media (e.g. Facebook, online forums, word of mouth etc...) and existing Happify users who have previously indicated they are parents of adolescents as part of the Happify onboarding process. We will also use a snowballing recruitment method, in which parents who complete the prescreener will be encouraged to share the study with others. We will continue recruiting until 800 participants have met inclusion criteria, successfully completed the baseline assessment, and have started the study.

b. **Inclusion Criteria:** Participants are those who are 13-17 years old, are located in the United States, are a new user of Happify, willing and able to complete the study activities, agree to potentially being selected for the waitlist comparison, agree to not discuss the study with friends or family, report elevated levels of perceived stress (PSS score of at least 14) and rumination (RRS-Brooding score of at least 10), and have a

parent who is willing to consent to the study. Participants are required to complete and pass the baseline assessment to be included in this study.

**c. Exclusion Criteria:** Participants may withdraw from the study or skip assessments at any time; however during the prescreening and/or baseline process, potential participants will be disqualified if they indicate:

- i. They are not 13-17 years old.
- ii. They reside outside of the United States
- iii. They have previously registered for or used Happify
- iv. They are not willing and able to complete the study activities
- v. They indicate that they are not willing to continue the study or refrain from downloading Happify if selected to be on the waitlist
- vi. They are not willing to use a mobile app or internet website
- vii. They do not agree to refraining from discussing the study with friends or family
- viii. They have a PSS score of below 14
- ix. They have an RRS-Brooding score of less than 10
- x. They do not agree to be contacted
- xi. Their parent does not consent to the study
- xii. Participants will also be excluded if they do not complete the baseline assessment, or if they do but fail at least 7/7 attention checks.

2. **Sample Size:** We will recruit 800 participants to be in this study, 400 in each condition.

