4 ANALYSIS SETS/POPULATIONS/SUBGROUPS

To be eligible for this study, the following criteria needed to be met:

- range in age from 13-17 years of age
- perceived stress scale (PSS) score greater than 14
- rumination-brooding subscale score of at least 10

We will create a subgroup of the treatment condition, stratified by those who did and did not average two activities completed per week. This threshold has been established in prior studies of the Happify app as a minimum needed for adults to benefit significantly from the program (e.g., Parks et al., 2018). We will examine descriptive statistics for these subgroups.

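### The protocol gives two conflicting sets of entry cut-offs for perceived stress and rumination, and nothing in the documents reconciles them

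*Protocol*

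**What the plan says.** Three places state the entry cut-offs.

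- **Protocol II.a.ii (Study Design).** The adolescent completes the PSS and RRS at prescreen "to ensure their scores are above thresholds (PSS $\geq$ 10; RRS $\geq$ 14"). At baseline the same adolescent "must continue to meet thresholds for perceived stress and rumination"; no separate baseline figures are given there.
- **Protocol III.b and III.c (Inclusion and Exclusion Criteria).** Participants must "report elevated levels of perceived stress (PSS score of at least 14) and rumination (RRS-Brooding score of at least 10"). The exclusion list repeats both figures: "They have a PSS score of below 14" and "They have an RRS-Brooding score of less than 10". On timing, it says that "during the prescreening and/or baseline process, potential participants will be disqualified if they indicate" any listed item.
- **SAP section 4.** Eligibility needed a "perceived stress scale (PSS) score greater than 14" and a "rumination-brooding subscale score of at least 10".

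Protocol II.b lists one RRS form as a study measure, the 5-item Brooding subscale of the short form. Protocol I.d places random assignment after the inclusion criteria are met and the baseline assessment is taken. Protocol II.a.iii says that the survey data of those who do not qualify are deleted.

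**The concern.** The figures 10 and 14 appear in both protocol sections, attached to opposite scales. That looks like a transposition, but no text says so, and the documents do not show which figures were programmed into the online prescreener.

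Entry cut-offs define whom the result describes. Here the two rules differ in opposite directions: II.a.ii is lower on PSS and, on the Brooding reading, higher on rumination. Followed literally, II.a.ii turns away adolescents whom III.b admits, and no later step brings them back. Because the data of those who do not qualify are deleted, anyone screened out this way could not be counted afterwards.

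**Working it through.** No power or sample size figure is involved, so the check sets the rules side by side.

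**Inputs.** Whole-number scores are assumed. RRS in Protocol II.a.ii is read as the Brooding subscale; this is also an assumption, supported by Protocol II.b.

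- Rule A (Protocol II.a.ii): PSS ≥ 10 and brooding ≥ 14.
- Rule B (Protocol III.b and III.c): PSS ≥ 14 and brooding ≥ 10.
- Rule C (SAP section 4): PSS > 14, that is 15 or more, and brooding ≥ 10.

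**Where they part.**

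- Passed by A, refused by B: PSS of 10, 11, 12 or 13 with brooding of 14 or more. That is four PSS values.
- Passed by B, refused by A: brooding of 10, 11, 12 or 13 with PSS of 14 or more. That is four brooding values.
- Passed by B, refused by C: PSS of exactly 14. C passes nobody whom B refuses.

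Neither A nor B contains the other. Worked cases, taking the same scores at prescreen and baseline:

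| PSS, brooding | A alone | B alone | A then B | C |
|---|---|---|---|---|
| 12, 15 | yes | no | no | no |
| 20, 12 | no | yes | no | yes |
| 14, 12 | no | yes | no | no |
| 14, 14 | yes | yes | yes | no |
| 15, 14 | yes | yes | yes | yes |

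**What follows under each possible deployment.**

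1. *Rule A alone.* Adolescents with PSS 10 to 13 could enter, and those with brooding 10 to 13 are screened out.
2. *Rule A at prescreen, then Rule B.* Nobody with PSS 10 to 13 at the Rule B step enters. Adolescents with prescreen brooding 10 to 13 who meet Rule B are still lost.
3. *Rule B alone.* Protocol III describes the population correctly, and only the wording of II.a.ii is wrong.

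**If RRS in II.a.ii means a longer form.** Its 14 and the 10 in III.b are then on different scales, and the rumination comparison above does not apply. The PSS conflict (10 against 14) remains.

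**Size.** The documents give no distribution of PSS or brooding scores, so these score ranges cannot be turned into a number or share of adolescents.

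**The case against.** **It may be a lenient prescreen followed by a stricter baseline.** For PSS this is not ruled out. The instruction to keep meeting thresholds gives no baseline number, and the timing phrase in III.c does not say which step uses which figure. The wording shows no sign of a deliberate two-stage rule, but a PSS prescreen at 10 confirmed at 14 would be harmless. For brooding the explanation fails, because there the prescreen is the stricter step.

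**RRS may not mean Brooding.** II.a.ii omits the word, whereas II.a.iii, II.b and III.b include it, and the appendix list names the Ruminative Responses Scale Short Form. The Brooding reading is the likelier one, since no other RRS form is listed as a measure, but the rumination half of this point stays conditional on it.

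**It is probably clerical.** That may well be so. Protocol III states its figures twice, and the SAP agrees on brooding. The SAP also cites a published protocol paper that is not among these documents. Still, nothing here shows what was deployed.

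**Stronger readings that the documents do not support.**

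- A reader might infer that adolescents with PSS 10 to 13 were enrolled. Passing II.a.ii is not stated to be sufficient: that section and I.d both also require the inclusion criteria to be met. Entry at PSS 10 to 13 arises only if Rule A was applied alone.
- A reader might infer bias between the arms. Eligibility is settled before random assignment, so whichever rule was used applied equally to both.
- A reader might infer that the SAP will drop participants with a PSS of 14. Section 4 recounts eligibility in the past tense and states no rule for removing anyone from the analysis. The difference is one score value and may be loose wording; II.a.ii itself describes a greater-than-or-equal sign as being above a threshold.

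**Conclusion.** Wrong as written: this is an internal inconsistency, not a design choice. The PSS cut-offs in Protocol II.a.ii and Protocol III conflict on any reading. The rumination cut-offs conflict provided that RRS in II.a.ii is the Brooding subscale. With whole-number scores the disagreement covers PSS 10 to 13 and brooding 10 to 13, and the consequence ranges from a wording correction to a materially different entry population, depending on what was programmed. The SAP discrepancy at PSS 14 is minor. The validity of the randomised comparison is not in question; the description of the population is. The change should be made because an entry threshold is misstated in at least one place and the check is inexpensive. Which cut-off is right is not judged here.

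**What to change.** 1. Establish from the survey logic which cut-offs, which RRS form and which inequality were applied at prescreen and at baseline. This settles the question directly.
2. Reconcile Protocol II.a.ii, Protocol III.b and III.c, and SAP section 4 to the rule actually applied, and report that rule.
3. Report how many randomised participants fall outside the Protocol III criteria. As supporting evidence only, give the number with baseline PSS 10 to 13, with PSS exactly 14, and with brooding 10 to 13, and the same counts on prescreen scores where these were kept. Scores can change between the two steps, so each count bears only on the rule applied at its own step.
4. Keep all participants in the primary analysis as randomised.

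The cost is one check of the survey logic, wording corrections in up to three places, and a few counts from data already held. Enrolment and the analysis model do not change.

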**b. Study Measures:**

- i. Usage statistics such as number of activities completed and number of active days will be collected.
- ii. Major assessments will consist of several validated and published scales that assess aspects of participants’ mental health, and information about the participant. All scales also have been used in previous peer-reviewed research with adolescents. Scales are listed below, and the full text of all scale items can be found at the end of this document.
  1. Perceived Stress Scale (PSS; Cohen, Kamarck & Mermelstein, 1983): 10-item measure of perceived stress

2. Ruminative Responses Scale (RRS) - Short Form - Brooding Subscale (Treynor, Gonzalez, & Nolen-Hoeksema, 2003): 5 items which measure moody pondering over 7 days
3. Life Orientation Test-Revised (LOT-R; Scheier & Carver, 1985), 10-item measure on optimism
4. Roberts UCLA Loneliness Scale (Roberts, Lewinsohn, & Seeley, 1993): 8-item measure of subjective feelings of loneliness and social isolation
5. PROMIS Pediatric Sleep Disturbance Scale - Short Form 4a (Yu et al., 2012): 4-item scale measuring the frequency of sleep disturbances over 7 days

iii. Other Outcomes

1. Happify Scale (proprietary scale, developed by [name]): 9-item measure of cognitive and emotional well-being. This scale is given every 2 weeks, as part of the Happify platform experience.
2. Student Life Satisfaction Scale (SLSS; Huebner, 1991): measures life satisfaction in school-aged children and adolescents; is only given during the baseline assessment in order to validate the Happify Scale with adolescents.
3. Shortened Positive and Negative Affect Schedule for Children (PANAS-C-S; Ebetsutani et al., 2012), which measures positive and negative emotions in youth; is only given during the baseline assessment for validation purposes.
4. Demographic Questions (baseline assessment only):
  - a. Race and Ethnicity Question: “What is your race or origin?” (check all that apply). Participants will select from, “American Indian or Alaska Native”, “Asian”, “Black or African American”, “Hispanic or Latinx”, “Native Hawaiian or Other Pacific Islander”, “White”, or “Some other race or origin”. Then participants will be asked if they identify with a race or origin that was not on the list, and if they select “yes”, participants will be asked to “Please specify”, and they will be given a text box to type in.
  - b. Gender Question (optional): Participants will be asked “What is your gender?” and they will be provided with a text box to type in their response.
  - c. Age: “What year were you born?” (text box to respond)
  - d. Parental Happify Usage: “To your knowledge, have either of your parents used Happify before?”; participants will

respond with “Not that I know of”, “Yes, one of my parents” or “Yes, both of my parents”

5. Schooling Question (at each assessment point): 1 item asking “What is your schooling situation right now?” Participants will select from “Fully in person”, “Fully online learning”, “Hybrid model”, “Homeschool”, or “Do not attend school.”
6. Self-Care App Use (at each assessment point): 1 item asking participants if they have used any self-care or wellness apps. If they indicate yes, they will be prompted with “Which apps?” in which they will type in their response.

iv. Participants will receive reminders if they have not completed these assessments on time, and if a participant has not completed an assessment within 7 days of its scheduled date, a member of the research team will reach out via text message or email (depending on their preferred mode of contact) to check in. We will remind them that they receive \$20 for every major assessment completed (after baseline) and receive a \$20 bonus for completing all four assessments.

